## 4.9 Schedule of assessments

Visit	1	2	3	4	5	6	7	8
		Consolidation Treatment: To mirror the participant's planned treatment pathway						
Visit Window (No. Weeks ± No. Days)	Baseline*	Cycle 1 (Day 0) -8days	Cycle 2/HSCT -8days	Cycle 3/ HSCT -8days	EOT	3months post EOT	Month 24 (post randomisation anniversary)	Annual follow up (up to 5 years) (post randomisation anniversary)
Informed consent	x							
Medical history	x							
Confirm patient eligibility	x							
Randomisation		x a						
BPUC only: 30minute BPUC appointment		x						
PPCP only: MDT care planning sessions		x	x	x				
PPCP only: Participant check in		x Weekly check in						
Questionnaire booklet	x		x	x	x	x	x	
Health resource use questionnaire			x	x	x	x	x	

Visit	1	2	3	4	5	6	7	8
		Consolidation Treatment: To mirror the participant's planned treatment pathway						
Visit Window (No. Weeks ± No. Days)	Baseline*	Cycle 1 (Day 0) -8days	Cycle 2/HSCT -8days	Cycle 3/ HSCT -8days	EOT	3months post EOT	Month 24 (post randomisation anniversary)	Annual follow up (up to 5 years) (post randomisation anniversary)
PPCP only: Clinical screening questionnaire booklet		x	x	x				
6minute Walk Test	x					x b	x b	
Performance status	x	x	x	x	x	x	x	
SARC-F & Calf circumference	x				x b	x b	x b	
Hand grip strength	x				x b	x b	x b	
Height	x							
Weight	x	x c	x	x	x	x	x	
Food diary e	x d	x ce	x e	x e	x e	x e		
Haematology and biochemistry f	x f	x cf PPCP only	x f PPCP only	x f PPCP only				
Adverse events / complications of treatment			x	x	x			

Visit	1	2	3	4	5	6	7	8
		Consolidation Treatment: To mirror the participant's planned treatment pathway						
Visit Window (No. Weeks ± No. Days)	Baseline*	Cycle 1 (Day 0) -8days	Cycle 2/HSCT -8days	Cycle 3/ HSCT -8days	EOT	3months post EOT	Month 24 (post randomisation anniversary)	Annual follow up (up to 5 years) (post randomisation anniversary)
Review participant logbook			x g PPCP only	x g PPCP only	x g PPCP only			
Onward referrals		x As required h						
Survival status						x	x	x

*\*Where possible, baseline assessments should be completed at the end of induction chemotherapy, on blood count recovery, prior to hospital discharge*

- a) Randomisation should occur at least 8 days prior to the planned start date of cycle one of consolidation chemotherapy.
- b) Blinded outcome assessor
- c) Where this has not been completed within 7 days of the first appointment (for participants randomised to PPCP only) this should be repeated.
- d) The Baseline food diary will be a 24hour recall only, completed via paper
- e) 3-day food diary, either completed via myfood24 or through paper food diaries
- f) U&Es, FBC, neutrophils, eGFR, LFTs, magnesium, corrected calcium, phosphate, CRP, vitamin D to be taken on blood count recovery
- g) Logbooks should be reviewed at each cycle of treatment, and a copy provided to the study team for participants on the PPCP arm only
- h) Onward referrals as required throughout the treatment phase, supported by the central PROPEL specialist team and local HCP.

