### 2.2.2 Secondary Outcomes:

- Emotional wellbeing: the Warwick-Edinburgh Mental Wellbeing Scale (WEMWBS) assesses participant's mental wellbeing and consists of 14 items, scored on a 5-point Likert scale score, giving an overall score [12].
- Anxiety and Depression: Patient Health Questionnaire 9-item (PHQ9) measures severity of depression and response to treatment. General Anxiety Disorder 7-item (GAD7) assesses the likelihood of the presence of the four most common clinical anxiety disorders [13, 14].
- Health-related quality of life:
  - FACIT F incorporates the 27 item FACT-G (Functional Assessment of Cancer Therapy – General) and measures four domains of health-related quality of life: physical, social, emotional and functional well-being.
  - EQ-5D-5L measures health status in 5 dimensions plus a visual analogue scale of self-rated health status [15].
- Physical function:
  - Performance Status: the Karnofsky Performance Scale Index allows patients to be classified as to their functional impairment, used in (p)rehabilitation [16].
  - The 6-minute walk test [17].
  - Hand grip strength [18].
- Incidence of sarcopenia: SARC-F [19]; calf circumference [20].
- Incidence of malnutrition: Utilising Malnutrition Universal Screening Tool (MUST) [21] and its determinants; % weight change, Body Mass Index (BMI), energy and protein intake (food diaries via myfood24) [22].
- Completion of consolidation treatment plan (chemotherapy +/- HSCT)
- Number of onward referrals to local services for 'specialist' therapies.
- Overall and relapse-free survival.
- Readmissions to hospital, ICU admission, number of transfusions, complications of HSCT, adverse events and serious adverse events.
- Costs, cost-effectiveness and utility: costs, health resource use and EQ-5D-5L.
- Process Evaluation: fidelity to intervention delivery and dose of intervention received for each component.
- Mechanisms of Action:
  - Psychological flexibility – is the mechanism of action for ACT, and the model within which all intervention methods are delivered. This will be measured with a shortened version (8-items) of the CompACT questionnaires [23]
  - Motivation – measured using 1-item from the COMB-Q adapted for each component (3-items total) [24].

All questionnaires being used for the patient reported outcomes have been previously validated or have been adapted from validated questionnaires to fit this specific context and patient group.

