#### **4.5 Allocation concealment**

Where possible, participant allocation should be concealed from the practitioners conducting the physical outcomes assessments throughout the trial. The practitioners conducting the physical outcomes assessments therefore should be different staff members to those supporting the intervention delivery. To maintain this allocation concealment, sites will divide staff members into two groups: 1) Those who support and deliver intervention and/or control (local intervention HCP); 2) Those who conduct physical outcome assessments (blinded physical outcomes assessor). Those in group 1 will be those that are permitted to receive notification at the point of randomisation revealing the participants allocation.

During the physical outcomes assessments, participants will be asked to not reveal their allocation to the assessing practitioner. If, however, an allocation is revealed, the practitioner will record this on the relevant CRF and inform the trial office on [[contact]](mailto:[contact]). If an allocation is revealed, we ask that where possible the practitioner is changed for the next assessment visit in order to maintain blinded outcomes assessments.

Sites may request a blinded ISF for the blinded practitioners to use, which will only contain the documents relevant to their role.

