#### **4.10 Follow-up assessments**

To limit the burden on participants, only primary outcome and key secondary outcome data will be collected prior to each cycle of chemotherapy and at end of treatment (EOT). EOT within the PROPEL trial will be defined as following blood count recovery after the final cycle of intensive consolidation treatment (either chemotherapy or HSCT), where possible prior to discharge or at the EOT clinic review. Primary and secondary outcomes will be assessed in person at 3 months follow up post end of treatment (either chemotherapy or HSCT) and at 24 months post randomisation. Follow-up data for relapse and death will be collected up to 5 years from trial entry.

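### Karnofsky status is listed as a physical-function outcome, but the schedule does not mark it for the blinded assessor and the protocol does not say who rates it

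*Protocol*

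**What the plan says.** Section 2.2.2 of the protocol lists three physical-function measures: Karnofsky, the 6-minute walk test and hand grip strength. Of the first it says: "Performance Status: the Karnofsky Performance Scale Index allows patients to be classified as to their functional impairment". The trial summary groups the same three.

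Section 4.5 sets the blinding rule: "Where possible, participant allocation should be concealed from the practitioners conducting the physical outcomes assessments throughout the trial". It divides site staff into those who support or deliver the intervention or control, who may learn the allocation, and those who assess physical outcomes, who should not. It does not list the measures that count as physical outcomes, and it does not name Karnofsky.

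The schedule in section 4.9 applies the rule through footnote b, "Blinded outcome assessor". The footnote is on "Hand grip strength" and on SARC-F/calf circumference at EOT, 3 months post EOT and month 24, and on the walk test at 3 months and month 24. The row headed "Performance status" has a plain mark at every visit.

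Section 2.1.2 lists performance status as an item separate from physical function. Section 4.10 adds: "Primary and secondary outcomes will be assessed in person at 3 months follow up post end of treatment", and again at 24 months after randomisation.

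**The concern.** Sites are likely to work from the schedule. When neighbouring rows are marked for the blinded assessor and this one is not, a site can fairly conclude that Karnofsky need not go to that assessor. The local practitioner who gives weekly check-ins to participants in the intervention arm only is then free to score it. A rating that involves judgement, made by someone who knows the allocation and has worked with one arm, is open to detection bias. An apparent functional benefit of the intervention could arise partly from the rater, and the analysis could not separate the two.

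**Working it through.** **The passages side by side**

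| Measure | Listed under physical function (2.2.2) | Recorded after baseline (4.9) | Footnote b |
|---|---|---|---|
| 6-minute walk test | yes | 3 months, month 24 | 2 of 2 visits |
| Hand grip strength | yes | EOT, 3 months, month 24 | 3 of 3 visits |
| Karnofsky | yes | cycles 1, 2 and 3, EOT, 3 months, month 24 | 0 of 6 visits |

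SARC-F/calf circumference, listed in 2.2.2 under sarcopenia, carries the footnote at 3 of 3 visits. The blinded assessor is scheduled at EOT, 3 months and month 24, so the assessor is already due to see the participant at 3 of the 6 post-baseline Karnofsky visits. No blinded assessor is scheduled at the three cycle visits.

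**Who rates it?** The protocol does not say. Two features of the schedule point to staff. Performance status has its own row, apart from the questionnaire booklet, and it is recorded at cycle 1, where no booklet is given. This is an inference.

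**Does section 4.5 cover it?** Read with 2.2.2, yes. Read with 2.1.2, which separates performance status from physical function, not clearly. Under the first reading the schedule lacks a mark. Under the second, an outcome apparently rated by staff has no blinding provision. Both readings call for an edit.

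**Possible size (illustration only)**

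Inputs:
- Ratings per arm: 300 × (1 − 0.20) = 240. The 300 and the 20% come from section 8.1, where they apply to the fatigue score; carrying them over to Karnofsky is an assumption.
- SD of Karnofsky: 12 to 15 points, assumed.
- Bias: 10-20% of intervention participants scored one 10-point step too high, assumed. This gives 0.10 × 10 = 1 point to 0.20 × 10 = 2 points.

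Formulas: SE = SD × √(2/240). False-positive rate = P(|Z + bias/SE| > 1.96), with Z standard normal.

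| SD | SE | Bias 1: bias/SE | Rate | Bias 2: bias/SE | Rate |
|---|---|---|---|---|---|
| 12 | 1.10 | 0.91 | about 15% | 1.83 | about 45% |
| 15 | 1.37 | 0.73 | about 11% | 1.46 | about 31% |

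The protocol gives no figure of its own for Karnofsky to reproduce. Its sample size concerns fatigue and is not affected by this point.

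**The case against.** A reader might infer that the schedule contradicts section 4.5. The documents do not support that. The rule is limited to what is possible and never names Karnofsky, and section 2.1.2 gives a basis for treating performance status as something other than a physical outcome. The passages are inconsistent and need reconciling.

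A reader might also infer that the protocol assigns the rating to the unblinded practitioner. It does not: a missing footnote assigns nobody. Section 2.2.1 says that treating specialists take no part in outcome assessment. That sentence sits under the primary outcome and does not clearly reach the local check-in practitioner, so it shows intent without closing the gap.

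Other objections stand in part:
- That Karnofsky is staff-rated is inferred, as set out above.
- Karnofsky is the only unmarked measure among the three under physical function, but not among all physical measurements: weight is also unmarked.
- The false-positive rates rest on an assumed bias that always runs one way, an assumed SD and a borrowed sample size. With fewer ratings at month 24, which deaths could well bring about, the rates would be lower.
- Using blinded ratings alone would have a price. Section 4.11 accepts that participants transplanted at a centre outside the trial may be followed remotely and that physical assessments may not be obtainable. Dropping every unblinded rating would exchange possible rater bias for missing data, probably more often after transplant.

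**Conclusion.** The point holds as an inconsistency that leaves one secondary outcome without clear protection against detection bias. Section 2.2.2 makes Karnofsky a physical-function measure, section 4.5 asks for blinded assessment of physical outcomes where possible, and the schedule does not carry this through at any of the three visits where the blinded assessor is already due. That Karnofsky is rated by staff is a reasonable reading of the schedule but is not stated.

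The reach is limited. The primary outcome is self-reported fatigue, and the Karnofsky value used for stratification is collected before randomisation; neither is affected. The rates of about 11-15% and 31-45% show what a bias of 1 or 2 points could do under the stated assumptions; they do not predict that such a bias will occur. The change should be made because it is cheap and removes an avoidable doubt about this outcome.

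**What to change.** 1. In section 4.9, add footnote b to the performance status row at EOT, 3 months post EOT and month 24.
2. In section 4.5, name Karnofsky as a physical outcome to be assessed blind where possible, and bring section 2.1.2 into line with 2.2.2.
3. State who rates Karnofsky at the cycle visits, where no blinded assessor is scheduled, and check that this fits the statement on treating specialists in section 2.2.1.
4. Base the main between-arm Karnofsky comparison on the three visits in item 1. Record on the CRF whether the rater was blinded. Keep an unblinded rating where no blinded one could be obtained, and add a sensitivity analysis restricted to blinded ratings.

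The cost is one footnote, a few sentences, one CRF field and a little more assessor time. No new staff or visits are needed, because the blinded assessor is already scheduled at all three visits.

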#### **4.10 Follow-up assessments**

To limit the burden on participants, only primary outcome and key secondary outcome data will be collected prior to each cycle of chemotherapy and at end of treatment (EOT). EOT within the PROPEL trial will be defined as following blood count recovery after the final cycle of intensive consolidation treatment (either chemotherapy or HSCT), where possible prior to discharge or at the EOT clinic review. Primary and secondary outcomes will be assessed in person at 3 months follow up post end of treatment (either chemotherapy or HSCT) and at 24 months post randomisation. Follow-up data for relapse and death will be collected up to 5 years from trial entry.

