### **2.2 Outcome measures**

#### **2.2.1 Primary Outcome:**

Fatigue will be measured by the FACIT-F [11], a validated 40-item measure that assesses self-reported fatigue and its impact upon daily activities and function. It is appropriate for self-reporting or interview, takes approximately 10-15 minutes to complete, and is based on a 5-point Likert-type scale. Treating specialists will have no role in assessments of outcomes.

The rationale for the selection of primary outcome was informed by our PPI panel who placed the highest need on addressing fatigue. There is an extensive literature describing the real burden of fatigue in people with acute leukaemia. Whilst other measures of QoL were

considered relevant, our PPI kept returning to fatigue as the outcome that mattered the most.

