#### **3.1 Inclusion criteria**

- Age  $\geq$  16 years, treated on adult AML pathway

And either:

- Diagnosis of either AML or MDS-EB2 (MDS with  $\geq$ 10% blasts in the bone marrow)
- In complete remission at completion of induction chemotherapy (defined  $<$ 5% blasts in bone marrow)
- Intention to undertake consolidation treatment (chemotherapy +/- HSCT),

*\* Patients undergoing Venetoclax based treatment are only eligible if a HSCT is planned.*

**OR**

[figure not shown]
- Relapsed AML who have achieved a further complete remission, with an intent to deliver further intensive consolidation treatment +/- HSCT.
- Access to the internet and an email address.
- Willing to use videoconferencing to undertake the appointments and sessions.

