#### **4.11 Referral to another centre for HSCT**

In the most part for this trial, consolidation chemotherapy and HSCT will occur at a single hospital site, and therefore intervention delivery and follow up data collection will be seamless. In cases where chemotherapy and HSCT are delivered at different sites, trial follow up may require collaboration with the transplanting centre.

Where the transplanting centre is also open to PROPEL, the recruiting centre should notify the PROPEL trials office as soon as possible and prior to HSCT, and a hospital transfer CRF should be completed. The PROPEL trials office will contact the transplanting centre and organise the participant to be transferred via the PROPEL database. Although informed consent is an ongoing process, the original signed informed consent form will remain valid and does not require re-signing at the transplant centre at the point of transfer. The PROPEL trial office can advise if your nearest transplant centre is also open to PROPEL.

Where the transplanting centre is not open to PROPEL, post HSCT follow-up will involve close communication between the referring and transplant hospital. Sites should make every effort to collect data and questionnaires remotely where the participant does not return to the referring hospital at the relevant timepoint. If physical outcome assessments cannot be collected, the reason for this should be documented on the relevant case report form. PROPEL specialists will be available to contact for advice, should the transplanting hospital have any questions about the care plan in place for participants on the PPCP arm.

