#### **4.12 Post-randomisation withdrawals, exclusions and moves out of region**

Participants may be discontinued from the trial treatment and/or the trial at any time without prejudice. Unless a participant explicitly withdraws their consent, they should be followed-up wherever possible and data collected as per the protocol until the end of the trial.

Patients may be withdrawn from their trial allocation at the discretion of the Investigator and/or Trial Management Committee. If a patient withdraws from their trial allocation, either by their choice or at the discretion of the investigator, they must be followed up in accordance with the protocol. For patients who are lost to follow-up, follow-up data should

continue to be collected from hospital or GP records, these patients should not be automatically withdrawn from the trial.

Patients moving away from the region of the local site should NOT be withdrawn from the trial. Should this occur, please contact the PROPEL Trial Office with the relevant details, and they will endeavour to assign the patient's follow-up to a site close to their new location.

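### In-person assessment is written for the self-reported primary outcome at 3 and 24 months, with a remote route for one situation only, which risks avoidable missing FACIT-F data

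*Protocol*

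**What the plan says.** Section 4.10 sets the mode of the two post-treatment assessments: "Primary and secondary outcomes will be assessed in person at 3 months follow up post end of treatment" "and at 24 months post randomisation" are the two timepoints, and one sentence governs primary and secondary outcomes alike.

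Other sections bear on this:

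- Section 2.2.1 says of FACIT-F: "It is appropriate for self-reporting or interview, takes approximately 10-15 minutes to complete".
- Section 3.1 makes "Access to the internet and an email address" a condition of entry, along with willingness to use videoconferencing.
- Section 4.9 gives the questionnaire booklet its own row. It is due at baseline, before cycles 2 and 3, at end of treatment (EOT), 3 months after EOT and at 24 months. The walk test, grip strength and calf circumference are separate rows, marked for a blinded assessor after baseline.
- Section 4.11 contains the only written remote route for questionnaires. Its setting is: "Where the transplanting centre is not open to PROPEL, post HSCT follow-up will involve close communication between the referring and transplant hospital". Its instruction is: "Sites should make every effort to collect data and questionnaires remotely where the participant does not return to the referring hospital".
- Section 4.12 says that participants who have not withdrawn consent should be retained: "they should be followed-up wherever possible and data collected as per the protocol". Those who move are to be reassigned to a nearer site. For those lost to follow-up it turns to hospital or GP records.

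**The concern.** FACIT-F needs no visit. The walk test, grip strength, calf circumference and weight do. Tying all of them to attendance means that a participant who cannot travel loses the primary outcome together with the physical tests, although a 10-15 minute questionnaire could have been sent to an email address that every participant must have.

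The written fallbacks do not close the gap. The rule in section 4.12 refers back to the protocol, and so to the in-person wording. Hospital and GP records would not ordinarily hold a FACIT-F score. Section 4.11 shows that remote completion is accepted as valid, but for one group only. Section 7.3 offers paper food diaries to participants who are unwell, so a secondary outcome has a fallback for illness that the primary outcome lacks.

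Two things are at stake. Avoidable loss uses up the 20% allowance. And if people stay away because they are ill or exhausted, the primary outcome is missing in relation to its own value.

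**Working it through.** **1. The plan's own figure.** The inputs, from section 8.1, are a standardised difference of 0.3, 90% power, two-sided 5%, 20% dropout and a two-sample t-test.

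- Required number analysed: 234.5, rounded up to 235 per arm.
- Inflated for dropout: 235 / (1 − 0.20) = 293.75, so 294 per arm and 588 in total.
- The stated 300 per arm (600) is this figure rounded up. It reproduces.

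**2. Power if loss differs from 20%.** Number analysed per arm = 300 × (1 − loss), same test, difference 0.3. Every loss other than 20% is an assumption.

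| Loss | Analysed per arm | Power |
|---|---|---|
| 20% (planned) | 240 | 90.7% |
| 25% | 225 | 88.8% |
| 30% | 210 | 86.6% |
| 35% | 195 | 84.0% |

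These figures describe loss from any cause. They do not show how much of it the in-person wording would produce.

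**3. Bias in an attenders-only comparison.** If non-attenders score lower than attenders by the same gap in both arms, then

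shift in the difference (PPCP − BPUC) = gap × (non-attendance in PPCP − non-attendance in BPUC).

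With an assumed gap of 8 points:

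- 12% v 17% non-attendance: 8 × (0.12 − 0.17) = −0.4 points, or 10% of the 4-point target.
- 10% v 20% non-attendance: 8 × (0.10 − 0.20) = −0.8 points, or 20% of the target.

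**4. Bias when missingness depends on the score itself.** This was simulated with a true difference of 4 points and SD 13 (section 8.1). The odds of being missing are multiplied by an assumed factor for each SD of worse fatigue. The table gives the unadjusted difference among completers, in points.

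| Overall missing | Factor 1 | Factor 1.5 | Factor 2 | Factor 3 |
|---|---|---|---|---|
| 20% | 4.03 | 3.93 | 3.77 | 3.52 |
| 30% | 4.03 | 3.90 | 3.71 | 3.40 |

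Factor 1 means no dependence on fatigue; its 4.03 against a true 4 shows a simulation error of about 0.03. In this model the bias is towards no difference.

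**5. What these figures are not.** Steps 3 and 4 concern a completers' comparison at one time. Section 8.2.1 plans a longitudinal mixed-effects model. The scores before cycles 2 and 3 and at EOT, which carry no in-person wording, would enter that model and recover part of the loss. Steps 3 and 4 therefore illustrate the mechanism and do not predict the bias of the primary analysis.

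**The case against.** The strongest reply is that section 4.10 describes the format of a visit at which physical tests are due anyway, and nothing in the protocol prohibits completing the booklet another way. A reader might infer that remote completion is forbidden outside section 4.11. The text does not say so. FACIT-F is described as suitable for self-report or interview, section 4.12 asks for follow-up wherever possible, and section 4.11 already treats questionnaires and physical tests differently. That part of the objection stands: the fault is a route that is not written, not a ban.

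A reader might also infer that the most fatigued participants will be the ones missing. The documents hold no data on missingness by fatigue. The inference is plausible: section 4.1 provides a short summary sheet for people too fatigued to read the full information sheet, and section 4.8 expects what participants can do to vary with how well they feel. It remains an inference. A supervised visit may even give better completion among those who come.

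Other points also stand. Section 1.1 quotes 20% survival at 5 years, so deaths may account for much of the missing 24-month data, and a change of mode recovers none of that. The mixed model helps, and section 8.2.1 says a sensitivity analysis on missing-data assumptions will be considered. Section 7.1 leaves requirements for form completion and return to a data management plan that is not shown.

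These points lower the expected size but do not remove the gap. A data management plan that allowed remote completion would still sit beside a protocol sentence that says in person. No analysis replaces questionnaires that were never collected if their absence depends on the unobserved score.

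**Conclusion.** The point holds as a weakness in how follow-up is fixed. Section 4.10 states in-person assessment for a self-reported primary outcome at both post-treatment timepoints, and a remote route is written for one situation only. Followed as written, this risks avoidable missing FACIT-F data, possibly related to illness and fatigue.

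The size cannot be taken from the documents. If total loss reached an assumed 30%, power at 0.3 would be about 86.6% against 90.7% at the planned 20%, a fall of 4.1 percentage points. Under the assumed mechanisms above, the completers' difference shrinks by a few tenths of a point up to 0.8 of the 4-point target. The planned model would recover part of that, but not all if missingness depends on the unobserved score.

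The figures do not support a conclusion that the trial is underpowered: 300 per arm reproduces, and the sample size is not in error. This is a cheap correction worth making, not a demonstrated failure of the primary analysis.

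**What to change.** In section 4.10, limit the in-person requirement to the physical assessments. Add that any participant in either arm who cannot attend may complete the questionnaire booklet, FACIT-F first, online, by post or by telephone within the visit window, with the mode of completion recorded on the CRF. Attendance can remain the default. This extends to everyone the route that section 4.11 already accepts.

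The cost is about one sentence in the protocol and one CRF field. The downside is mixed modes of completion, which can be examined in a sensitivity analysis because the mode is recorded. No change to the sample size is needed.
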